8.7 DMC Meeting Minutes

Minutes of all meetings will be prepared by the DMC Secretary.

The DMC minutes for open and closed meeting sessions will be circulated to the DMC members for comments within 5 business days after a meeting. If comments/confirmation are not received within 5 business days, except for a pre-specified reason from a DMC member, it will be assumed there are no comments. At the same time, the minutes for the open sessions will be circulated to the Sponsor for comments. If the DMC has a recommendation for action, this will be outlined in the open session minutes with any rationale. The DMC Secretary will incorporate the comments and then route the final minutes to the DMC members for approval signatures.

Each DMC member will be provided with final copies of the complete summary meeting minutes by the DMC Secretary and the Sponsor will be provided with a final copy of the open session meeting minutes with DMC recommendations.

At the end of the study, the DMC Secretary will forward to the Sponsor Contact a complete set of summary meeting minutes (including both open and closed sessions).

8.8 Ad hoc Meetings

An emergency meeting of the DMC may be called at any time by the Chair should questions of subject safety arise. The request will be sent to the DMC Administrator, who will then schedule and organize the meeting and meeting materials. Further data review meetings in addition to those already planned may be required based on study enrollment extending beyond the planned duration of the 2 trials.

Ad hoc specialists can be invited to DMC meetings as recommended by the DMC or uniQure.

9. AMT-061 DOSE CONFIRMATION FOR PHASE III TRIAL

At their first safety data review meeting, the DMC will confirm if the dose of 2×10^{13} gc/kg AMT-061 used in the Phase IIb study CT-AMT-061-01 is suitable for administration in the Phase III study CT-AMT-061-02, in addition to reviewing the study safety.

In addition to safety data, the DMC will be provided with the 6 week interim efficacy data from CT-AMT-061-01 to review prior to the meeting. The DMC will evaluate response to treatment with a single dose of 2×10^{13} gc/kg of AMT-061 in terms of FIX activity levels and assess whether observed FIX activity levels are $\geq 5\%$.

Following their review, the DMC has the responsibility to provide a recommendation to Sponsor concerning the dose of 2×10^{13} gc/kg AMT-061, either confirming this dose is suitable for use in the Phase III study or to suggest further evaluation. If the DMC determines that the observed response is not within the expected range, or they do not observe enough consistency of effect to proceed to Phase 3 dosing, they can elect to recommend up to three more subjects be treated at the same dose or recommend a second dose be studied.

Anticipated recommendations concerning the dose of AMT-061 are as follows:

- Proceed with dosing in CT-AMT-061-02 with a single treatment of 2×10^{13} gc/kg AMT-061
- Treat 1, 2, or 3 additional subjects at the dose of 2×10^{13} gc/kg AMT-061 and reevaluate the data
- Evaluate a second dose of AMT-061

This recommendation will be in addition to a safety recommendation as per [Section 8.5](#).

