In addition to the above, the continuous accumulation of clinical data from the use of AAV5 in hemophilia subjects suggests that AAV5 is associated with a very low risk of inducing immune responses that may lead to loss of the newly induced endogenous factor IX protein expression. Furthermore, low titers of pre-existing antibodies against AAV5 (using a highly sensitive assay), which may demonstrate neutralization of AAV5 transduction in in-vitro assays, have no apparent inhibitory effect in human studies at currently administered dose levels. As a consequence, future trials with AMT-061 (including this trial) will allow enrolment of subjects even in the presence of anti-AAV5 antibodies.

The strong efficacy (protein expression) and safety results obtained during the Phase 1/2 trial with AMT-060 demonstrate 2 x 10^{13} gc/kg to be the optimal dose for use in future trials in terms of safety and efficacy. In addition, accumulated clinical and non-clinical data support the implementation of the prospectively defined product enhancement of AMT-061 at 2 x 10^{13} gc/kg for the pivotal trial. The primary aim of this trial is to confirm that a single dose of 2 x 10^{13} gc/kg AMT-061 will result in factor IX activity levels of \geq 5%. An objective of the trial is to assess whether observed factor IX activity levels are within an expected range, to determine if 2 x 10^{13} gc/kg AMT-061 is suitable from efficacy point of view for administration in the pivotal Phase 3 trial. In addition, the safety profile of AMT-061 will be demonstrated.

Investigational Medicinal Product, Dose, and Mode of Administration:

The investigational medicinal product (IMP) is identified as AAV5-hFIXco-Padua (AMT-061; etranacogene dezaparvovec). AMT-061 is a recombinant AAV5 containing the Padua variant of a codon-optimized human factor IX complementary deoxyribonucleic acid (cDNA) under the control of a liver-specific promoter. The pharmaceutical form of AMT-061 is a solution for IV infusion.

The single administered dose of AMT-061 is 2×10^{13} gc/kg. The subjects will be monitored for tolerance to the IMP and detection of immediate AEs for 24 hours (overnight stay) after dosing. The dosing of the subjects must be separated by a minimum of 14 calendar days to allow for subject safety monitoring and to ensure appropriate action can be taken in case any acute reactions are observed.

Trial Design/Methodology:

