transgene activity is approximately 6 times higher per unit protein for AMT-061 as compared to AMT-060. Although the study design only included a direct comparison at 5 x 10^{12} gc/kg, it can be expected that plasma exposure, liver distribution, liver cell transduction and transgene expression behave similarly at each dose level with a range. As expected, the study demonstrated that for the same dose, the mean factor IX protein of AMT-060 (average of 4.89, ranging from 3.17 to 7.61 %) and AMT-061 (average of 4.85, ranging from 2.92 to 6.17 %) was comparable. The confirmation of transgene activity being approximately six times higher per unit protein (average of 6.10, ranging from 5.41 to 7.47 %) can similarly be expected to result in multiple of the already demonstrated activity levels of AMT-060 within a range. These results are comparable to the increase in gain-of-function reported for the Padua factor IX protein compared with "wild-type" factor IX protein in animal models (Crudele et al., 2015; Monahan et al., 2015).

The observed translation of the NHP for AMT-060 to the clinical Phase 1/2 for AMT-060 supports the translation of the NHP study for AMT-061 (NR-061-17-001, Study No. NC1615) to further inform the dose rationale for the proposed dose confirmation trial with 2×10^{13} gc/kg AMT-061. At 2 x 10^{13} gc/kg, AMT-061 is predicted to result in mean factor IX activity ranges of 40% of normal, with acceptable ranges (between approximately 18-76%) within the expected safety for factor IX replacement with an upper range well below the cut off of 129%.

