3.2 Trial Design Rationale

In gene therapy it is common practice to provide a single dose of vector via IV infusion. This infusion in a previous trial with AMT-060 was proven to be safe and effective resulting in identification of a clincial dose for AMT-060 to proceed to further clinical studies. Although this resulted in successful conversion of clinical phenotype to mild in most subjects, the desired goal is to achieve higher levels of factor IX activity to allow for a more consistent and meaningful clinical response. This trial will investigate AMT-061 at the identified dose for AMT-060 ($2 \times 10^{13} \text{ gc/kg}$).

This is the first trial with the gene product AMT-061 in humans. As AMT-061 is an isolated modification of the wild-type human factor IX in AMT-060, it is expected that the safety of this product improvement will be similar as the safety characteristics that have been described for AMT-060 at a dose of 2×10^{13} gc/kg. Also, clinical benefit of AMT-060 was achieved at this dose (refer also to Section 1.4 for a description of the Phase 1/2 trial). Therefore, a similar dose of AMT-061 will be used in this trial. Based on NHP studies with AMT-061, as well as data from patients with the natural Padua mutation, it is expected that the modified product AMT-061 will lead to a higher level of circulating factor IX activity at comparable levels of factor IX protein and thereby increase the likelihood of alleviating the need for exogenous therapy,

including the need for on-demand treatment of traumatic bleeds and selective prevention of a bleed (e.g., because of upcoming physical activity, sports, etc.). At $2 \ge 10^{13}$ gc/kg, AMT-061 is expected to result in mean factor IX activity ranges of 40% of normal, ranging between approximately 18-76%.

This trial is conducted at multiple centers as the prevalence of severe and moderately severe hemophilia B subjects is low.

Due to the nature of the disease in question it is not ethical to perform a placebo-controlled trial and no relevant active comparators exist. Based on this the trial is designed as an open-label and uncontrolled trial.

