9.12 Data Monitoring Committee

A data monitoring committee (DMC) will be involved in the management of the overall AMT-061 program including this clinical trial. The purpose of the DMC in this trial is to monitor safety of the subjects in the trial as well as to evaluate response to the treatment in terms of factor IX activity levels. The DMC will assess whether observed factor IX activity levels are within an expected range to determine if the administered dose is suitable for administration in a pivotal phase 3 trial (range to be defined in DMC charter). If the DMC determines that the observed response is not within the expected range, or they do not observe enough consistency of effect, to proceed to Phase 3 dosing they can elect to recommend up to three more subjects be treated at the same dose or recommend a second dose be studied. DMC meetings will be held at set times during the trial as outlined in the DMC charter. Further details regarding the DMC can be found in the DMC charter, which will be available prior to the administration of IMP.

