8.6 Recommendation Letter

Following each safety data review meeting, the DMC will submit a letter to the Sponsor outlining their recommendations for the study. The DMC Secretary will facilitate the drafting of the letter, based on the DMC recommendations discussed and agreed upon during the closed session. If there is a recommendation for action, the brief rationale for such recommendation will be included in the letter. The DMC Recommendation Letter will be sent to the DMC Chair for review, approval, and signature following the meeting (no later than 1 working day after the DMC meeting). The DMC Secretary will then provide a copy of the final signed Recommendation Letter to the Sponsor Contact, Principal Investigator, and the DMC Administrator on the DMC Chair's behalf via email. If the recommendation letter is not provided to the Sponsor on the same day as the meeting, the DMC Secretary will provide the Sponsor with the DMC members' recommendation decision via email.

The Sponsor will be responsible for communicating to the Investigators, IRBs, and/or other regulatory bodies, as appropriate, a summary of the DMC recommendation(s) and the Sponsor's proposed action.

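### Does the DMC Charter leave the expected factor IX range for the Phase 3 dose recommendation undefined?

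*SAP*

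**What the plan says.** Protocol 9.12 has the DMC compare observed factor IX activity with an expected range, to decide whether the dose is "suitable for administration in a pivotal phase 3 trial (range to be defined in DMC charter"). The synopsis, in its rationale, says much the same: "An objective of the trial is to assess whether observed factor IX activity levels are within an expected range".

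The DMC Charter, filed with the SAP, treats the decision in section 9. The committee reviews the six-week data "in terms of FIX activity levels and assess whether observed FIX activity levels are" at least 5%. The following paragraph lets it recommend up to three more subjects at the same dose, or a second dose, if "the observed response is not within the expected range, or they do not observe enough consistency of effect to proceed to Phase 3 dosing". That paragraph gives no limits. Charter section 5, item 9, refers the dose decision to section 9, and sections 3 and 11 and Appendix 3 add no figure.

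Elsewhere the protocol gives a two-sided prediction. Section 3.2 says the dose is "expected to result in mean factor IX activity ranges of 40% of normal, ranging between approximately 18-76"%. Section 1.3.1 speaks of "acceptable ranges (between approximately 18-76%) within the expected safety for factor IX replacement with an upper range well below the cut off of 129"%.

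**The concern.** The protocol promises a range, and the visible charter delivers a floor and then uses the word range again without tying the two together. The only activity range that the protocol gives for AMT-061 in humans is 18-76%. Section 1.3.1 puts it forward to "further inform the dose rationale for the proposed dose confirmation trial with" AMT-061, which is this trial. A reader could therefore take the expected range to be at least 5%, or 18-76%, or anything below 129%.

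The decision has consequences. Charter 4.2 allows three subjects to become six, and Charter 4.3 makes Phase 3 dosing wait for confirmation of the dose. A 5% floor shows a minimal response. By itself it neither tests the roughly sixfold gain in activity per unit of protein described in Protocol 1.4 nor flags unusually high activity.

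**Working it through.** **1. The texts side by side.**

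| Place | Figure | Role given to it |
|---|---|---|
| Protocol 2.1; SAP 2.2.1 | at least 5% | primary objective at six weeks |
| Protocol 9.12 | none | range left to the charter |
| Charter 9, criterion | at least 5% | what the DMC assesses |
| Charter 9, next paragraph | none | ground for more subjects or a second dose |
| Charter 10 | below 5% | poor response in the neutralizing-antibody rule |
| Protocol 1.3.1 and 3.2 | about 18-76%, mean 40% | prediction |
| Protocol 1.3.1 | 129% | upper cut-off set against that prediction |

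The criterion in Charter 9 has the same structure as the sentence in Protocol 9.12: the DMC assesses whether observed activity satisfies a condition. The charter puts at least 5% where the protocol put the range. The later mention of the range reads most simply as referring back to it. No visible passage gives 18-76% or 129% to the DMC as a limit.

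**2. Where 18-76% probably comes from.** Protocol 1.3.2.2 reports AMT-060 high-dose subject means of 3.1 to 12.7%, with an overall mean of 7.1%. Multiplying by the predicted gain of 6:

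- 3.1 × 6 = 18.6%
- 7.1 × 6 = 42.6% (protocol: 40%)
- 12.7 × 6 = 76.2%

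This agrees closely with the protocol's figures. The derivation is an inference, since the documents do not state it. It suggests that the band carries forward the spread of five earlier subjects and was not written as a decision rule.

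**3. Do the readings differ?** They can. With the same inputs, a gain of 5 / 3.1 = 1.61 (1.61 / 6 = 27% of the prediction) brings the lowest subject to 5%. A gain of 129 / 12.7 = 10.2 takes the highest subject to 129%. Hypothetical Week 6 results:

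| Results (%) | All at least 5% | All within 18-76% | All below 129% |
|---|---|---|---|
| 6, 8, 12 | yes | no | yes |
| 30, 80, 110 | yes | no | yes |
| 20, 40, 135 | yes | no | no |

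**4. Would 18-76% work as a test that every subject must pass?** Assume log-normal activity with AMT-060 median √(3.1 × 12.7) = 6.27%. Take the SD of the log as ln(12.7 / 3.1) / 2.326 = 0.606, where 2.326 is the expected range of five normal values in SD units. At exactly the predicted gain the median is 6.27 × 6 = 37.6%. One subject falls inside 18-76% with probability Φ(1.16) − Φ(−1.22) = 0.765, and all three do with probability 0.765³ = 0.45 (0.80 with SD 0.4, 0.25 with SD 0.8). A product that performed as predicted would miss such a test about half the time. The inputs are means over 52 weeks in five subjects, so this is only an illustration.

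**5. What the DMC has besides the floor.** SAP 6.2 tabulates the ratio of activity to protein at the same six-week interim, which measures the gain directly. It places the shells for that analysis in Charter Appendix 4, which Charter 11 identifies as the DMC Data Report. Charter 11 also lists activity levels, so high values are visible. Charter 9 lets the DMC act on insufficient consistency and requires a separate safety recommendation under section 8.5. Charter 6 leaves the final decision to the Sponsor, and SAP 3.3 lets subjects be added on sponsor recommendation as well.

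**6. What a clarification would change.** SAP 6.7.1 describes the Week 6 and Week 52 data-cut analyses in the past tense, and SAP 6.1 says that the 12-month report followed an earlier SAP. The trial's analyses are descriptive. No estimate, table or count depends on how the range is worded.

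**The case for a change.** The best argument for a change is that the synopsis gives the primary aim as at least 5% and then adds the expected range as an objective of its own. If the two were identical, the second sentence would be redundant. Charter 10 shows that this committee's charter can write explicit criteria when it wants them. Nor need the record resolve the matter. Charter 8.6 says: "If there is a recommendation for action, the brief rationale for such recommendation will be included in the letter". A plain recommendation to proceed might arguably carry no reasons.

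The textual part of this stands. The visible charter does not define the term or say whether it has an upper side.

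The rest is weaker. Restating the same threshold in synopsis prose is common and does not establish a second rule. The point about the letter supposes that advice to proceed with Phase 3 dosing is not a recommendation for action, although Charter 9 lists it among the anticipated recommendations. Charter 8.7 also provides minutes of the closed sessions, which go to the Sponsor at the end of the study. The concerns about the sixfold gain and about high activity treat the 5% figure as if it were the whole review, which step 5 shows it is not.

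**Conclusion.** No change to the plan is called for. The gap is one undefined term in a committee document. The surrounding text points to the 5% criterion, and the committee had the data and the discretion to look beyond it. A rule written now would be retrospective, because the review it governed has taken place, and the number of computed results affected is zero.

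This rests on reading Charter 9 together with Protocol 9.12 and the primary objective. Some charter pages and the separate report shells are not available here, and a fuller definition may stand there; that would only narrow the gap. Nothing here says which activity limit would be the right one for the dose decision.

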10. NEUTRALIZING ANTIBODIES

The DMC will assess whether there is an impact of pre-existing NAB titers on clinical outcome following treatment with AMT-061. Should the DMC determine that there is a recognizable impact of a certain titer and above, they can recommend institution of an exclusion criterion based on these titers for further enrollment in the study.

The DMC will review data after every set of approximately 10 subjects enrolled depending on enrollment rates (enrollment will not stop during this review). Review of this data will be

included in the safety data review meetings or in NAB-specific data review meetings, depending on the timing of the review due to the rate of enrollment. NAB review meetings may be combined and include multiple set of 10 subjects due to a high rate of enrollment. Ad hoc meetings may be called if there is a safety concern, impacted outcomes, or need for a protocol amendment. During their review, the DMC will provide one of the following assessments:

- No clear impact, continue with prospective analysis
- There are impacted outcomes (safety and/or efficacy), institution of a data-driven cut-point
- Protocol amendment needed

An enactment of a NAB titer cut-off mid-trial is recommended if all of the following criteria are met:

- Two patients with NAB titers and FIX <5%
- No patients with NAB titers equal or greater to NAB titers in patients with FIX \geq 5%
- No patients without NAB titer and FIX <5%

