8.5 DMC Recommendations

Based upon their review and discussion of the safety data at each meeting, the DMC has the responsibility to recommend to the Sponsor whether the study should proceed as planned, be modified, or be stopped.

Anticipated recommendations are as follows:

- Continue the studies according to the protocols and current amendments.
- Temporarily stop enrollment in the CT-AMT-061-02 study to investigate a safety issue.
- Modify the study protocol(s) and/or the informed consent.
- Stop the studies due to an urgent situation (serious safety issue).

If the DMC detects a safety signal or has concerns about the provided data in the DMC Data Report or other safety information, they may request additional safety-related information from the Sponsor Contact or designee.

Modifications recommended by the DMC may include, but are not limited to, changes in the exclusion criteria due to NABs (see [Section 10](#)), other changes in the inclusion/exclusion criteria, frequency of safety monitoring, and instituting changes in the study procedures. While modifications are put into place, enrollment would continue in the CT-AMT-061-02 study unless the DMC also recommends for a temporary stop.

In the case that the DMC recommends to stop the studies or to temporarily halt enrollment in CT-AMT-061-02, the DMC Chair will notify the Sponsor Contact immediately. If the Sponsor needs additional clarification, the Sponsor Contact, or designee, and the DMC members will meet as quickly as possible to discuss the recommendations.

If the DMC recommends to stop the studies, the Sponsor's response would be to place study recruitment on hold pending final decision by the Sponsor. Investigators, Institutional Review Boards (IRBs), and other Regulatory Authorities will be notified by the Sponsor, as appropriate.

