11. DATA REPORTS FOR REVIEW BY THE DMC

For each data review meeting, the DMC Data Reports will be provided to each DMC member by the DMC Secretary via a suitable secure method for their prior review. The report will be delivered approximately 10 business days before each DMC meeting.

The DMC Data Report for the DMC includes the tables, figures, and listings (TFLs) to be reviewed by the DMC members at the scheduled and/or ad hoc meetings. Mock-ups of the report format and content (i.e., TFL shells) are provided for CT-AMT-061-01 in [Appendix 4](#) and for CT-AMT-061-02 in [Appendix 5](#). The Sponsor and DMC members will review and approve the format and content of the mock-up DMC Data Report prior to the first DMC data review meeting.

The following descriptive summaries and listings will be included in the DMC Data Report based on the cumulative data in the study.

- Baseline demographic tables and results of the number of subjects screened, randomized or discontinued (with reasons for discontinuation) for the study
- List of frequent AEs (>5%) listed in order of frequency, from high to low and summarized of all SAEs and AEs leading to study discontinuation
- Summaries of all potentially clinically significant (PCS) laboratory results and vital signs
- Summaries of increases in alanine aminotransferase (ALT) and aspartate aminotransferase (AST)
- NAB titer
- Capsid-specific T-cells
- FIX activity levels

A subset of these outputs will be provided for DMC review after every set of approximately 10 subjects enrolled, for assessment of the impact of NABs. This subset of outputs will be identified in the DMC Data Report shells.

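### Criterion 2 of the DMC Charter's neutralising-antibody cut-off rule conflicts with the section's aim as written, and SAP 6.2 splits a Week 6 table by antibodies to FIX where the question is AAV5

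*SAP*

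**What the plan says.** DMC Charter Section 10 lets the committee recommend a titre-based exclusion: "Should the DMC determine that there is a recognizable impact of a certain titer and above", it may ask for one to apply to further enrolment. It then gives a specific trigger: "An enactment of a NAB titer cut-off mid-trial is recommended if all of the following criteria are met". The three criteria are:

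1. "Two patients with NAB titers and FIX <5"%.
2. "No patients with NAB titers equal or greater to NAB titers in patients with FIX" ≥5%.
3. "No patients without NAB titer and FIX <5"%.

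SAP 6.2 plans, for the Week 6 interim analysis, a table of FIX activity for patients with and without pre-existing neutralising antibodies directed at FIX. The next sentence plans a scatter plot of Week 6 FIX activity against the baseline titre of neutralising antibodies to AAV5. Protocol 1.5.2 poses the pre-existing-antibody question for AAV5. Protocol 4.2 excludes anyone with a history of FIX inhibitors (criterion 1) or a positive inhibitor test at screening (criterion 2).

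**The concern.** The trigger is meant to identify a titre at and above which treatment fails. For that, failures should sit at the high end of the titre scale and responders below them. Criterion 2 as worded takes the responders' titres as the reference and does not say which patients are compared with them. Committee members could apply opposite rules to the same data, and the record could not show whether the criteria had been met.

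The SAP 6.2 table has a simpler fault. It names the wrong antibody, so one of its two groups should contain nobody and the table cannot address the question that the protocol asks.

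**Working it through.** **Criterion 2.** Call patients with FIX ≥5% responders and those with FIX <5% failures. Take criterion 1 as at least two failures with a titre, and suppose criterion 3 is satisfied. Five readings of criterion 2 are possible.

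Literal (the reference is responders' titres):
- L1: no patient of any kind has a titre at or above a responder's titre.
- L2: no failure has a titre at or above any responder's, so all failures lie below the lowest responder.
- L3: no failure has a titre at or above the highest responder's.

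Aim-consistent (FIX ≥5% attached to the opening words, as the FIX condition is in criteria 1 and 3):
- A1: no responder has a titre at or above any failing titre, so all responders lie below the lowest failure.
- A2: no responder has a titre at or above the highest failing titre.

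L1 cannot be met once any responder has a titre, because that patient's titre equals itself. Such a patient is not hypothetical. Protocol 1.5.2 reports that the AMT-060 subject with the highest titre, 1/340, also had the highest FIX activity of the cohort. Protocol 1.3.2.2 gives the highest subject means as 6.8% (low dose) and 12.7% (high dose), both above 5%.

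*Illustrative titres* (assumed, except 340):

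| Failures | Responders with a titre | L1 | L2 | L3 | A1 | A2 |
|---|---|---|---|---|---|---|
| 700, 900 | 50, 340 | no | no | no | met | met |
| 20, 30 | 340, 700 | no | met | met | no | no |
| 100, 900 | 340 | no | no | no | no | met |
| 700, 900 | none | met | met | met | met | met |

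Row 1 is the pattern that the section seeks, and every literal reading stays silent. Row 2 is the opposite pattern, and two literal readings call for a cut-off.

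*Ordering count.* With 2 failures and m responders, all with untied titres, there are C(m+2, 2) orderings.
- L1: 0.
- L2: failures hold the two lowest ranks, 1 ordering.
- L3: no failure holds the top rank, C(m+1, 2) orderings.
- A1: failures hold the two highest ranks, 1 ordering.
- A2: a failure holds the top rank, m+1 orderings.

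| m | Orderings | L1 | L2 | L3 | A1 | A2 |
|---|---|---|---|---|---|---|
| 1 | 3 | 0 | 1 | 1 | 1 | 2 |
| 2 | 6 | 0 | 1 | 3 | 1 | 3 |
| 4 | 15 | 0 | 1 | 10 | 1 | 5 |

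L2 and L3 require a responder at the top rank; A1 and A2 require a failure there. So once any responder has a titre, no ordering satisfies both a literal and an aim-consistent reading. At m = 4, L3 and A2 split all the orderings between them: 10 + 5 = 15.

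Even the aim-consistent form is incomplete. In row 3 of the first table, A1 blocks the cut-off and A2 permits it.

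**SAP 6.2.** Take neutralising antibodies to FIX to be FIX inhibitors. Exclusions 1 and 2 then remove patients known to have them, so the expected size of the antibody-positive group is 0 of 3. The next sentence of SAP 6.2 and Protocol 1.5.2 both name AAV5, so FIX is probably a slip for AAV5, though the documents do not confirm it.

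**The case against.** The best defence of criterion 2 is that a committee of haemophilia experts would read it in the light of the aim stated in the same section. L1 defeats itself as soon as one responder has a titre, which is a reason not to suppose it was meant. Which reading comes most readily is a matter of judgement, and I do not rest the point on it. What stands is that every literal reading conflicts with the aim and that the aim-consistent one still needs a word added.

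The trigger also does not act alone. Section 10 separately offers "institution of a data-driven cut-point" as an assessment, and Section 8.5 allows "changes in the exclusion criteria due to NABs". Section 11 supplies the committee with titres and FIX activity: "A subset of these outputs will be provided for DMC review after every set of approximately 10 subjects enrolled". Under Section 8.4 a recommendation to modify the conduct of a study must be unanimous, and under Section 6 the sponsor decides whether to implement it. All of this stands and limits the harm.

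The rule has almost no role in this trial. It governs further enrolment, reviewed about every 10 subjects. Charter 4.2 gives this trial 3 subjects, possibly 6, and Protocol 13.3 records that all were approaching Month 30 at the February 2021 amendment. The rule matters for the Phase III trial of about 56 subjects (Charter 4.3) under the same charter.

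On SAP 6.2, the Week 6 analysis is past (SAP 6.7.1 describes it in the past tense). The AAV5 scatter plot and Listing 4.8.2 of AAV5 titres already show individual values, which for three subjects is most of what a table could give. That also stands.

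**Conclusion.** Both points are wrong as written, and both are minor. Criterion 2 conflicts with the aim of its own section under each literal reading, and the one form that fits leaves open whether any failing titre or only the highest is meant. The ordering counts assume untied titres, exactly two antibody-positive failures and no antibody-negative failure. They assume nothing about how titre affects outcome.

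Three stronger inferences should not be drawn:

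- **That a harmful titre would go undetected, or the wrong patients be excluded, in Phase III.** The discretion, the unanimity rule and the sponsor's decision stand between the wording and any such result. A probability that the rule misfires would need an assumed titre effect. The documents give none; Protocol 1.5.2 reports that pre-existing titres had no predictive value.
- **That criterion 2 can never be met.** All five readings are met when no responder has a titre.
- **That the issued Week 6 table is wrong.** SAP 6.2 places its shells in Charter Appendix 4, which refers to a separate document not available here. They may already say AAV5.

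**What to change.** In DMC Charter Section 10, the sponsor should reconcile criterion 2 with the section's stated aim. It should say which patients' titres are compared with which, and whether the comparison is with any failing titre or with all of them (the highest). Whether a cut-off should exist, and at what titre, is outside this point.

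In SAP 6.2, change FIX to AAV5 as the target of the neutralising antibodies in the table description. Then check the Week 6 shell and the issued interim table, and correct the record if either carries the same wording.

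The cost is a few words in the charter, one word in the SAP, and a check of one shell and one table. No new data are needed.
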